Toxicokinetic data were obtained from Good Laboratory Practice (GLP) 4-week repeated dose studies in rats and dogs. In rats, exposure was slightly less than dose-proportional after oral administration. In dogs, the toxicokinetics showed a more than dose proportional increase in AUC_{0-24h} and C_{max} (5–20 mg/kg).

Summary of Toxicology Data

A comprehensive battery of repeated dose studies was conducted, in which, emodepside was orally applied (in diet) for up to 13 and 14 weeks in mice and rats, respectively, at doses up to 1000 ppm and 800 ppm (1000 ppm equals in mice

approx. 245-380 mg/kg, 800 ppm equals in rats approx. 77-95 mg/kg, both in 13-week treatment schedule).

The studies in rats revealed toxicities resulting from metabolic changes induced by emodepside indirectly, such as a decrement in bodyweight gain, but, in parallel, an increased feed and water consumption as well as deformation of teeth as a sign of a diabetic-like effect. The main affected organs were kidney, pancreas and liver, with associated changes in haematological parameters, triglyceride and glucose levels in the plasma and lipid and glycogen stores. These toxicological findings pointed to a diabetes-related condition (inhibition of insulin secretion followed by increased glucose levels and reduced leptin levels, as confirmed by mechanistic studies). In mice, the NOAEL after 14 weeks of treatment was 50 ppm (10.5-16.8 mg/kg). The NOAEL in the 14-week rat study was defined at 10 ppm (m: 0.73, f: 1.11 mg/kg per day); In 4-week rat studies 50 ppm (equals 4–5 mg/kg) was defined as the NOAEL.

In dogs, doses starting from 10 mg/kg per day for 4 weeks resulted in clinical signs like vomiting, tremor and unsteady gait. At 20 mg/kg, an effect on nutritional state, food intake and bodyweight gain was noted. All effects were reversible after a recovery period of 4 weeks. The NOAEL for this study was 5 mg/kg.

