12.4 Values of Potential Clinical Importance

Any laboratory value outside the reference interval for that variable will be flagged with an 'H' if it is higher than the reference interval, and with an 'L' if it is lower. Additionally, if, during the course of the trial, a variable changes from baseline (Day 0 pre dose) by more than a predetermined amount (as defined by the Principal Investigator, Appendix A), that value will receive a flag 'I' if increased, or 'D' if decreased. Therefore, if a value both falls outside the reference interval and alters from the baseline value by more than the predetermined amount, it will attract a double flag and will be considered to be potentially clinically important.

A vital signs result will be considered to be of potential clinical importance if it falls outside the relevant range below:

Vital Sign	Range
Supine/semi-recumbent systolic blood pressure	85–160 mm Hg
Supine/semi-recumbent diastolic blood pressure	40–90 mm Hg
Supine/semi-recumbent heart rate	35–100 beats/min
Respiration rate	8–20 per min
Oral temperature	35.5–37.8°C

QT, QTcB or QTcF > 450 msec and increases in QT, QTcB or QTcF from baseline of > 30 msec will be considered to be potentially clinically important.

13 Study Population

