16.2.6.1.3	Listing of emodepside plasma urine sample collections	L PK2 PG
16.2.6.1.4	Individual emodepside plasma concentration-time plots for estimation of λ_z , with regression line	F PK10
16.2.6.2.1	Listing of PD concentration-time data	L PK1 PG
16.2.7	Adverse events	
16.2.7.1	Listing of all adverse events	L AE1 PG
16.2.7.2	Listing of serious adverse events	L AE1 PG
16.2.7.3	Listing of adverse events leading to withdrawal from study	L AE1 PG
16.2.8	Laboratory values	
16.2.8.1	Listing of clinical chemistry abnormalities of potential clinical importance	L LB1 PG
16.2.8.2	Listing of all clinical chemistry laboratory data for subjects with PCI	L LB2 PG

Listing	Description	Template (Shells below)
	abnormalities*	
16.2.8.3	Listing of haematology abnormalities of potential clinical importance	L LB1 PG
16.2.8.4	Listing of all haematology laboratory data for subjects with PCI abnormalities*	L LB2 PG
16.2.8.5	Listing of urinalysis data	L URI PG
16.2.9	Vital signs, ECG variables and physical findings	
16.2.9.1	Listing of vital signs of potential clinical importance	L VS1 PG
16.2.9.2	Listing of ECG values of potential clinical importance	L EG1 PG
16.2.9.3	Listing of abnormal ECG findings	L EG2 PG
16.2.9.4	Listing of abnormal physical examination findings	L PE1 PG
16.2.9.5	Listing of abnormal neurological examination findings	L NE1 PG
16.2.9.6	Listing of abnormal ophthalmology examination findings	L PE1 PG

* ICH does not require full listings of lab data so only subjects with double-flagged values will be listed.

Complete listings of all data collected in this study will also be produced.

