Appendix A: Laboratory Ranges

Pre-determined Changes for Laboratory Data (from FL140 v4)

Test	Test Code	Unit	Sex	Delta ranges	
				Acceptable decrease	Acceptable increase
Activated partial thromboplastin time	APTTT	sec	Both	- 8.0	+ 8.0
Alanine transferase	ALTN	IU/L	F	-	+ 30
Alanine transferase	ALTN	IU/L	M	-	+ 30
Albumin	ALB	g/L	Both	- 8	+ 8
Alkaline phosphatase	ALPN	IU/L	Both	- 30	+ 30
Amylase	AMY	U/L	Both	-	+ 150
Aspartate transferase	ASTN	IU/L	F	- 30	+ 30
Aspartate transferase	ASTN	IU/L	M	- 30	+ 30
Basophils	BASO	10 ⁹ /L	Both	-	+ 0.30
Bilirubin conjugated	DBIL	µmol/L	Both	-	+ 4.0
Bilirubin total	TBIL	µmol/L	F	- 20.0	+ 10.0
Bilirubin total	TBIL	µmol/L	M	- 20.0	+ 10.0
Bilirubin unconjugated	IBIL	µmol/L	Both	-	-
C-reactive protein	CRP	mg/L	Both	-	-
CK relative index	CKMBR	%	Both	-	-
Calcium	CA	mmol/L	Both	- 0.4	+ 0.4
Carbon dioxide	CO2	mmol/L	Both	- 8	+ 8
Chloride	CL	mmol/L	Both	- 10	+ 10
Cholesterol	CHOL	mmol/L	Both	-	+ 0.7
Creatine kinase	CK	IU/L	F	-	+ 400
Creatine kinase	CK	IU/L	M	-	+ 400
Creatinine	CREA	µmol/L	Both	-	+ 40
Creatinine (DOA urine)	CREDA-U	mmol/L	Both	-	-
Eosinophils	EOS	10 ⁹ /L	Both	-	+ 0.50
Erythrocyte sedimentation rate	ESR	mm/h	Both	-	-
Fibrinogen	FIB-C	g/L	Both	-	-
Free T3	FT3	pmol/L	Both	- 3.5	+ 3.5
Free T4	FT4	pmol/L	Both	- 15.0	+ 15.0
Gamma glutamyl transferase	GGT	IU/L	F	-	+ 40
Gamma glutamyl transferase	GGT	IU/L	M	-	+ 40
Globulin	GLOB	g/L	Both	- 8	-
Glucose	GLU	mmol/L	Both	- 1.5	+ 2.5
Haematocrit	HCT	L/L	Both	- 0.050	-
Haemoglobin	HB	g/L	Both	- 20	-
High density lipoprotein	HDL	mmol/L	Both	- 1.50	+ 1.50
International normalised ratio	INRR	ratio	Both	-	-
Lactate dehydrogenase	LDH	IU/L	Both	-	+ 150
Lymphocytes	LYMP	10 ⁹ /L	Both	- 1.50	+ 1.50
Magnesium	MG	mmol/L	Both	-	-
Mean cell haemoglobin	MCH	pg	Both	- 2.0	+ 2.0
Mean cell haemoglobin concentration	MCHC	g/L	Both	- 25	+ 25
Mean cell volume	MCV	fL	Both	- 10	+ 10

Test	Test Code	Unit	Sex	Delta ranges	
				Acceptable decrease	Acceptable increase
Monocytes	MONO	10 ⁹ /L	Both	- 0.50	+ 0.50
Neutrophils	NEUT	10 ⁹ /L	Both	- 2.00	+ 8.00
Phosphate	PHOS	mmol/L	Both	- 1.00	+ 1.00
Platelets	PLT	10 ⁹ /L	Both	- 100	+ 100
Platelets (citrate tube)	PLTC	10 ⁹ /L	Both	- 100	+ 100
Potassium	K	mmol/L	Both	- 0.8	+ 0.8
Prolactin	PROL	µg/L	Both	-	-
Prothrombin time	PTT	sec	Both	- 4.0	+ 4.0
Red blood cells	RBC	10 ¹² /L	Both	- 1.0	-
Reticulocyte	RET	%	Both	-	-
Reticulocyte count	RETC	10 ⁹ /L	Both	-	-
Reticulocyte manual count	RETM	10 ⁹ /L	Both	-	-
Sodium	NA	mmol/L	Both	- 8	+ 8
Thrombin time	TT	sec	Both	-	-

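### Eight protocol-named blood tests have no change limit in SAP Appendix A, so the table and listings of potentially clinically important laboratory values can never report them

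*SAP*

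**What the plan says.** SAP 12.4 gives an H or L to any result outside its reference interval. A second flag, I or D, is given when the result moves from the Day 0 pre-dose baseline "by more than a predetermined amount (as defined by the Principal Investigator, Appendix A"). PCI status needs both: "if a value both falls outside the reference interval and alters from the baseline value by more than the predetermined amount", then "it will attract a double flag and will be considered to be potentially clinically important". Protocol 10.6.2 has the same rule. Neither document gives another route to PCI status or says what happens when a test has no limit.

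The limits are in SAP Appendix A, headed "Pre-determined Changes for Laboratory Data (from FL140 v4"). Some rows carry no limit in either direction, for example those beginning "Magnesium MG mmol/L Both" and "Prolactin PROL µg/L Both", which end in two dashes.

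Three outputs depend on the rule. Table 14.3.4 (template T_LB1) counts only the double flags HI and LD; its programming note extends it to all tests, groups and time points, with n as the number of results. Listings 16.2.8.1 and 16.2.8.3 show PCI values for chemistry and haematology. Listings 16.2.8.2 and 16.2.8.4 give full panels for subjects who have such a value. The footnote in SAP 18.1 explains the restriction: "ICH does not require full listings of lab data so only subjects with double-flagged values will be listed".

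**The concern.** A rule that needs two conditions cannot be met when one of them is undefined. For a test without a change limit, the PCI count is zero before any sample is drawn. Table 14.3.4 would still print that zero beside a genuine number of results, and a reader could not tell it from a zero that means the test was screened and nothing was found.

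Safety is the primary objective, and SAP 4.2.1 places these laboratory tests among the primary endpoints. Several of the eight bear on the non-clinical findings. Protocol 1.3 says of the rat studies: "The main affected organs were kidney, pancreas and liver". Lipase is a pancreatic enzyme and GLDH a liver enzyme. The same section reports reduced leptin and prolactin and a diabetes-like condition, to which HbA1c is relevant.

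**Working it through.** The plan states no figure to reproduce, so the check is a row-by-row match and a count.

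**Inputs.** The blood tests in protocol 2.2.2, with the white-cell differential split into five cell types; the rows of SAP Appendix A; the sampling times in note 15 of the schedule of events.

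**Step 1: analytes named.** Haematology 15 (including the differential and HbA1c), coagulation 2, biochemistry 28, additional hormones 2. Total: 15 + 2 + 28 + 2 = 47.

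**Step 2: match to Appendix A.**

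| Limit in Appendix A | Analytes | Count |
|---|---|---|
| No row | lipase, GLDH, LDL, HbA1c, leptin | 5 |
| Row, dashes in both directions | magnesium, prolactin, reticulocytes (all three reticulocyte rows) | 3 |
| Limit in one direction only | haemoglobin, haematocrit, RBC, eosinophils, basophils, ALT, GGT, LDH, CK, amylase, total cholesterol, triglycerides, creatinine, conjugated bilirubin, total protein | 15 |
| Limits in both directions | the rest | 47 − 5 − 3 − 15 = 24 |

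Tests with no limit at all: 5 + 3 = 8 of 47 (8/47 = 17%).

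**Step 3: apply the rule.** PCI = (H and I) or (L and D). With no limit in either direction, neither I nor D can be assigned, so PCI is impossible whatever the value.

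**Step 4: footprint in Table 14.3.4.** Note 15 gives 11 sampling times after the Day 0 pre-dose baseline: Days 1, 5, 8, 9, 10, 14, 23, 30, 60, 90 and 120. Five of the eight tests (lipase, GLDH, LDL, magnesium, reticulocytes) belong to the routine panels: 5 × 11 = 55 rows per treatment group. Leptin and prolactin add one row each (Day 9), and HbA1c adds one (Day 120) if the protocol schedule is followed: 55 + 2 + 1 = 58 rows per treatment group. With complete data each would show n = 6 in an emodepside group and a forced zero. This assumes that all eight tests are reported in the table. The template note says all tests, but the SAP does not name the table in which leptin, prolactin or HbA1c will appear.

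**Step 5: is the flag baseline available?** SAP 12.4 fixes it at Day 0 pre-dose. Leptin and prolactin are sampled at Screening Visit 1 and Day 9 (protocol 2.2.2 and the schedule notes), although protocol 8.4.3 says Day −1 and Day 9. HbA1c has a screening value only before dosing. None of the three has a Day 0 value, so adding limits alone would not make the rule work for them unless the more general fallback in SAP 12.2 is taken to override 12.4.

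**Step 6: HbA1c timing.** SAP 4.2.1 says HbA1c is measured at screening only; protocol 2.2.2 says screening and Day 120. Under the SAP wording there is no post-dose value to flag.

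**The case against.** The strongest reply is that laboratory reporting does not rest on the PCI flag. A reader might infer that abnormal values of these eight tests would go unflagged and unseen. The documents do not support that. Under SAP 12.4 an H or L needs no Appendix A limit. SAP 18.1 also promises complete listings of all data, and the chemistry and haematology tables (template T_LB2) give minimum, maximum and change from baseline, so an extreme value would show. Listings 16.2.8.2 and 16.2.8.4 would include these tests for any subject who qualifies through another test. Protocol 8.5.5 has clinically significant abnormalities reported as adverse events under stated conditions. All of this stands, and it confines the defect.

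A reader might also infer that the target organs are left out of PCI screening. They are not: ALT, AST, alkaline phosphatase, GGT and bilirubin have limits for the liver, amylase for the pancreas, creatinine and urea for the kidney. Glucose has limits too, and its own pharmacodynamic tables. Lipase and GLDH add to organs already covered.

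It can be said that the dashes are the Principal Investigator's choice. That is plausible for the three dashed rows, since dashes recur throughout the appendix. It does not explain five absent rows. The table carries female rows in an all-male trial and tests that this protocol does not name, such as ESR and fibrinogen, which suggests a general site list not fitted to this study. Even a deliberate choice not to screen a test should not be printed as zero.

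**Conclusion.** The point holds within limits. Eight of 47 protocol-named blood analytes cannot become PCI under SAP 12.4 and protocol 10.6.2, and cannot by themselves bring a subject into listings 16.2.8.1 to 16.2.8.4. Followed literally, Table 14.3.4 shows uninformative zeros for them, up to 58 rows per treatment group. The fault lies in the PCI table and PCI listings, not in laboratory safety reporting as a whole. It should be corrected because those outputs are the plan's screening summary for laboratory safety.

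The conclusion assumes that a dash means no limit was set. The SAP does not define the dash, but nothing in it suggests that any change would count. The five tests with no row do not depend on that reading. It also assumes that no rows were lost from Appendix A in the text available; the table is alphabetical and shows no visible break where the five would fall.

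**What to change.** Before unblinding:

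1. Have the Principal Investigator add change limits to Appendix A for the eight tests.
2. State in SAP 12.4 that the flag baseline for leptin, prolactin and HbA1c is the screening value, because they have no Day 0 value. Reconcile protocol 8.4.3 (Day −1) with the other sections (Screening Visit 1) at the same time.
3. Reconcile the HbA1c schedule between SAP 4.2.1 and protocol 2.2.2.
4. For any test still without a limit in either direction, print *not assessed* in Table 14.3.4 instead of zero.

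An alternative to step 1 is to let an out-of-range value alone count as PCI where no limit exists. It must be restricted to tests with no limit in either direction. Otherwise it would also catch the 15 one-sided analytes, turning a low ALT or a high haemoglobin into a PCI value. It would also need H and L columns in template T_LB1 and a note in the SAP that it departs from protocol 10.6.2. Step 1 avoids both.

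The cost is up to eight table entries, a few sentences in the SAP, a small template change and a few more flagged values. No sampling changes, provided that the Day 120 HbA1c sample in the protocol is kept.

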Appendix B: Pharmacokinetic Analysis

1 Calculation Methods

1.1 Data Handling Conventions

1.1.1 Actual v Planned Times

Actual sample times will be used for the calculation of pharmacokinetic parameters and for individual concentration-time plots.

Planned sampling times will be used to calculate the concentration-time summary statistics and summary concentration-time plots.

1.1.2 Missing and BQL Concentrations

No missing values will be imputed.

For calculation of all pharmacokinetic parameters and individual profile plots, plasma concentrations below the limit of quantification of the assay (BQL) will be treated as missing (except BQL values observed before the maximum concentration, which will be taken as zero).

BQL values observed post dose will be substituted by one half of the lower limit of quantification for the calculation of concentration summary statistics. Pre dose values will be taken as zero. The number of imputed values will be included in the summary tables.

For urine concentrations reported as BQL it is not possible to impute a value. The amount excreted will be set to zero when concentration is BQL.

1.2 AUC Calculations

The AUC will be calculated by a combination of linear and logarithmic methods. The linear trapezoidal method will be employed for all incremental trapezoids arising from increasing concentrations and the logarithmic trapezoidal method will be used for those arising from decreasing concentrations.

AUC_(0-∞) values with <20% of this area extrapolated will be reported.

It is acceptable to include data from profiles with >20% extrapolated as long as at least 80% of the profiles in the study have <20% of the AUC_(0-∞) as extrapolated area. In this instance, individual plasma concentration-time profiles for which the extrapolated areas are >20% of AUC_(0-∞) will be identified.

It is unacceptable to use AUC_(0-∞) data if >40% of the AUC has been extrapolated, except in specific situations which should be carefully justified in the study report.

1.3 Lambda-z Calculations

The apparent terminal phase rate-constant (λ_z) will be estimated by linear regression of logarithmically transformed concentration versus time data. Only those data points which are judged to describe the terminal log-linear decline will be used in the regression.

During the analysis, repeated regressions are carried out using the last three points with non-zero concentrations, then the last four points, last five, etc. Points prior to C_{max} are not used. Points with a value of zero for the concentration are excluded. For each regression, an adjusted R² is computed. The λ_z using the regression with the largest adjusted R² is selected. If the adjusted R² does not improve, but is within 0.0001 of the largest adjusted R² value, the regression with the larger number of points is used. λ_z must be positive, and calculated from at least three data points.

A minimum number of three data points will be used in calculating λ_z .

For non-compartmental analysis uniform weighting will be applied.

If non-linear regression (i.e. compartmental) analysis is used then weighting by y^{-1} or y^{-2} should be investigated.

Justification for rule: The log transformation of the data in calculation of λ_z sufficiently deals with the heterogeneous variability of the concentration data and no further weighting is necessary.

1.4 Observed v Predicted Values

For parameters dependent on λ_z , the ‘predicted’ rather than the ‘observed’ parameters will be calculated.

The ‘predicted’ parameters are calculated using \hat{C}_t (the predicted value of the concentration at time t_n); whilst the ‘observed’ parameters use the last observed concentration.

2 General Considerations for Data Analysis

2.1 Derived and transformed data

A list of those parameters that will be log transformed will be given in the SAP.

In general, concentration and concentration-related quantities, rate constants and half-lives (e.g. C_{max} , AUC, $t_{1/2}$, CL/F, V_z/F and MRT) will be analysed after logarithmic transformation. Logarithmic transformations will use natural logarithms (\log_e).

If t_{max} is subjected to a statistical analysis, it will not be transformed and will be analysed using non-parametric methods (Cartwright et al.(1991)).

2.2 Summary data

Means at any time will only be calculated if at least 2/3 of the individual data are measured and are above the lower limit of quantification (LLOQ).

3 Parameter Definitions

3.1 Plasma Parameters

3.1.1 Single Dose

Emodepside parameters to be calculated on Day 0.

Text Symbol	Definition	Calculation	Typical Units	Log Transform	WNL	CDISC Controlled Terminology	TFL Symbol
Concentrations and times							
C_{max}	Maximum (peak) plasma concentration	The maximum (peak) plasma concentration will be obtained directly from the concentration-time data.	ng/mL	Y	Cmax	CMAX	C_{max}
$C_{max}/Dose$	Dose-normalised AUC to infinity	The dose-normalised C_{max} will be calculated as $C_{max}/Dose$ administered	(ng/mL)/mg	Y	Cmax_D	CMAXD	C_{max}/D
$C_{max,norm}$	Observed maximum plasma concentration corrected by dose and body weight	The C_{max} normalised by dose and body weight will be calculated as $C_{max}/(Dose\ administered * body\ weight)$	(ng/mL)/(mg*kg)	Y	-	CMAXWD	$C_{max,norm}$
t_{max}	Time to reach maximum (peak) plasma concentration	The first time of maximum (peak) plasma concentration will be obtained directly from the concentration-time data.	h	N	Tmax	TMAX	t_{max}
Areas under the curve							
AUC_{12}^*	Area under the plasma concentration-time curve from time zero to time 12 h	The area under the concentration-time curve from zero time (pre-dose) to time 12 h will be calculated using the (specified) trapezoidal method. If λ_z is not estimable, a partial AUC is not calculated (when $t_{last} < t$).	h*ng/mL	Y	User specified area	AUCINT	AUC_{12}
$AUC_{12}/Dose^*$	Dose-normalised AUC from time zero to 12 h	The dose-normalised AUC from time zero to 12h will be calculated as $AUC_{12}/Dose$ Administered	(h*ng/mL)/mg	Y	-	AUCINTD	AUC_{12}/D
$AUC_{12,norm}^*$	Area under the concentration-time curve from time zero to 12h corrected by dose and body	The AUC from time zero to 12h normalised by dose and body weight will be calculated as $AUC_{12}/(Dose\ administered * body\ weight)$	(h*ng/mL)/(mg*kg)	Y	-	AUCINTWD	$AUC_{12,norm}$

Text Symbol	Definition	Calculation	Typical Units	Log Transform	WNL	CDISC Controlled Terminology	TFL Symbol
	weight						
AUC ₂₄ **	Area under the plasma concentration-time curve from time zero to time 24 h	The area under the concentration-time curve from zero time (pre-dose) to time 24 h will be calculated using the (specified) trapezoidal method. If λ_z is not estimable, a partial AUC is not calculated (when $t_{last} < t$).	h*ng/mL	Y	User specified area	AUCINT	AUC ₂₄
AUC ₂₄ /Dose **	Dose-normalised AUC from time zero to 24 h	The dose-normalised AUC from time zero to 24h will be calculated as AUC ₂₄ /Dose Administered	(h*ng/mL)/mg	Y	-	AUCINTD	AUC ₂₄ /D
AUC _{24, norm} **	Area under the concentration-time curve from time zero to 24h corrected by dose and body weight	The AUC from time zero to 24h normalised by dose and body weight will be calculated as AUC ₂₄ /(Dose administered*body weight)	(h*ng/mL)/(mg*kg)	Y	-	AUCINTWD	AUC _{24, norm}
Clearance, volume of distribution and mean residence time							
V _z /F	Apparent volume of distribution during terminal phase after non-intravenous administration	Apparent volume of distribution will be calculated using the following formula: $V_z / F = \frac{Dose}{\lambda_z \cdot AUC_{\infty}}$	L	Y	V _z _pred (actually derives V _z _F_pred for oral dose)	VZFP	V _z /F
MRT _{last}	Mean Residence Time	The mean residence time will be calculated using: $MRT = \frac{AUMC}{AUC_{\infty}}$	h	Y	MRTLST_pred	MRTEVLST	MRT _{last}

* Calculated only for Cohort 3

**Calculated only for Cohorts 1 and 2

